Primary Hypothesis: The Smart System VR Headset (M&S Technologies, Niles, IL) will perform as well as or better than the Humphrey Visual Field Analyzer (Carl Zeiss Meditec Inc., Dublin, CA) in identifying glaucomatous visual field changes.

I.6 Background and significance and/or Preliminary studies related to this project. (do not indicate "see protocol")

Glaucoma is the leading cause of irreversible blindness worldwide (1-2). Standard Automated Perimetry with the Humphrey Visual Field Analyzer (HFA; Carl Zeiss Meditec Inc., Dublin, CA) is the current accepted clinical standard for diagnosis and monitoring of glaucomatous visual field loss (3). Despite ubiquitous use, the HFA has several disadvantages that limit its utility. The HFA is a large, expensive device that requires dedicated clinic space. It is immobile, so bedside examination and home monitoring are not possible. Additionally, it is difficult for patients with limited mobility or large body habitus to comfortably position themselves for the duration of the exam. Recently, there has been interest in development of a head-mounted virtual reality perimeter to address these limitations (4-6).

I.7 Literature cited / references (if attaching a grant or protocol enter N/A).

- 1. Quigley HA. Number of people with glaucoma worldwide. Br J Ophthalmol. May 1996;80(5):389-93. doi:10.1136/bjo.80.5.389

II. Research Team

II.1 Principal Investigator

Name E-mail College
[name] Carver College of Medicine

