• 🗸	Repository – The collection, storage, and distribution of human biologic samples and/or data materials for research purposes. Repository activities involve three components: (i) the collection of data and/or specimens such as blood, tissue, saliva, etc.; (ii) the storage of data or specimens, and data management function; and (iii) the sharing of data/specimens with recipient investigators other than the original investigators. (paraphrased from OHRP)
•	Other
1.a i	Does this project involve any of the following (Check all that apply):
	• Phase I trials – include initial studies to determine the metabolism and pharmacologic actions of drugs in humans, the side effects associated with increasing doses, and to gain early evidence of effectiveness; may include healthy participants and/or patients (ClinicalTrials.gov & FDA)
	• Phase II trials – include controlled clinical studies conducted to evaluate the effectiveness of the drug for a particular indication or indications in patients with the disease or condition under study and to determine the common short-term side effects and risks(ClinicalTrials.gov & FDA)
	• Phase III trials — include expanded controlled and uncontrolled trials after preliminary evidence suggesting effectiveness of the drug has been obtained, and are intended to gather additional information to evaluate the overall benefit-risk relationship of the drug and provide an adequate basis for physician

labeling(ClinicalTrials.gov & FDA)

- Phase IV trials studies of FDA-approved drugs to delineate additional information including the drug's risks, benefits, and optimal use(ClinicalTrials.gov & FDA)
- VII.B.2 Does this project involve a drug washout (asking subject to stop taking any drugs s/he is currently taking)?
 No
- VII.B.6 Will any subjects receive a placebo in this study when, if they were not participating, they could be receiving an FDA-approved treatment for their condition?

 No
- VII.B.11 Is there a separate, written protocol that will be submitted in addition to this IRB New Project form? (Note: a grant application is not considered to be a protocol)

 No
 - VII.B.18 Does this project involve the evaluation, or testing, of the safety and/or efficacy of a medical device? Yes
 - VII.B.19 Describe in detail procedures in place for maintaining device shipment and receipt records:

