- VII.E.5 Does this project involve creating any audiotapes, videotapes, or photographs?
- VII.E.6 Provide a detailed description in sequential order of the study procedures following the consent process DO NOT cut and paste from the Consent Document.

Describe study populations separately if they will be participating in different procedures - include CONTROL population if applicable.

DESCRIBE:

- What subjects will be asked to do/what happens in the study (in sequential order)
- The time period over which procedures will occur
- The time commitment for the subject for individual visits/procedures
- Long-term followup and how it occurs

Potential subjects will be approached at the time of their regularly scheduled appointment to participate in this research study. The research assistant will answer any questions potential subjects may have regarding the purpose, procedure, and risks of the study. If they agree to participate, subjects will sign an informed consent.

In addition to routine clinical examination including measurement of visual acuity, tonometry, and slit lamp examination, subjects will undergo perimetry with both the Smart System VR Headset (SSVR) and the Humphrey Field Analyzer (HFA). If the subject requires pupillary dilation during their appointment, visual field testing (VF) will be conducted prior to dilation. Subjects will be randomized to perform either the SSVR VF followed by the HFA VF or vice versa. Both VF will occur on the same day with a 15-20 minute break between tests at the University of Iowa Hospitals and Clinics' Glaucoma clinic. The total additional time commitment of study participation is expected to be 1-2 hours.

The SSVR Headset uses a 24-2 examination protocol with a Neighborhood-Zippy Estimation by Sequential Testing (ZEST) testing algorithm. Background brightness will be set to 15.8 ASB. The test will use Goldmann size III stimulus. The research assistant will administer the SSVR VF. The SSVR VF will be deemed unreliable if FP >25%. The HFA uses a 24-2 examination protocol with a SITA standard testing algorithm. A clinical technician will administer the HFA VF. The HFA VF will be deemed unreliable if FP >15%. After completing both VF tests, subjects will complete a satisfaction survey regarding the SSVR.

VII.E.7 Will you attempt to recontact subjects who are lost to follow-up?

No - those lost to followup will not be recontacted

VII.E.9 Will subjects be provided any compensation for participating in this study?

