 investigator's office by a research team member where they will be stored in a locked file cabinet until the conclusion
 of the study.
 - Electronic records (computer files, electronic databases, etc.) All electronic files will be kept as files on an encrypted, password-protected UIHC Department of Ophthalmology network server. There will be no identifiers or link available on any transferred data; therefore, there will be no way to compromise patients' privacy or confidentiality. M&S Technologies receives subject demographic and testing data upon completion of testing using the Smart System VR Headset. This data is stored in a secure, encrypted, HIPAA-compliant database. Subject names are not stored. Instead, Subjects receive encrypted ID codes.
 - Name -
 - Title Senior IT Support Consultant
 - University Job Classification Faculty/Staff
- X.5 Do the confidentiality protections indicated above allow only members of the research team to access the data/specimens?

X.6 Describe

M&S Technologies, the developers of the Smart System VR Headset visual field test, maintain a secure, encrypted, HIPAA-compliant database of patient testing information. This database includes study ID (de-identified), birth year, and experimental visual field testing data. M&S Technologies does not have access to any additional patient information.

X.7 Does your study meet the NIH criteria for a Certificate of Confidentiality or will you be applying for Certificate of Confidentiality?

No

XI. Data Analysis

XI.1 Describe the analysis methods you will use, including, if applicable, the variables you will analyze Variables: Clinical data including age, gender, ethnicity, visual acuity, intraocular pressure, Humphry Visual Field performance, Smart System VR Visual Field performance, and satisfaction survey will be collected and analyzed.

Data analysis: Humphrey Visual Field and Smart System VR Visual Field performance will be analyzed using pointwise comparisons grouped according to the Garway-Heath structure-function map.

XI.2 Provide the rationale or power analysis to support the number of subjects proposed to complete this study. Power analysis calculation summary:

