Sample sizes of 80 on device one (Smart System VR Headset) and 80 on device two (Humphrey Field Analyzer), which were obtained by sampling 40 clusters for device one and 40 clusters for device two with an average of 2 subjects per cluster, achieve 87% power to detect a difference between the device means of at least 0. The standard deviation of subjects is 0.25. The intracluster correlation coefficient is 0.500. A test based on a mixed-model analysis is anticipated at a significance level of 0.050. Here we view cluster one as testing using device one before device two and cluster two as testing on device two before device one.

A full version of the power analysis calculation has been attached as an additional document to the IRB - there was some difficulty with formatting when transferring this calculation from our statistician's text document to the IRB form.

XII. Future Research

- XII.1 Do you wish to keep any information about subjects involved with this research project so that members of the current research team may contact them in the future for your own research projects?

 No
- XII.2 Do you wish to keep any information about subjects involved with this research project so that other researchers may contact them for future research?

 No
 - XII.4 Does this project involve storing any data, tissues or specimens for future research? Yes—contribution for future use is mandatory for participation in the study

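### The hypothesis is that the headset is at least as good as the Humphrey analyzer, but the plan has only unranked grouped comparisons and a test for a difference, with no primary contrast and no margin

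*Combined protocol and SAP*

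**What the plan says.** - **I.5, primary hypothesis.** The headset "will perform as well as or better than the Humphrey Visual Field Analyzer" in identifying glaucomatous visual field changes. No margin is given.
- **XI.1, analysis methods.** After a list of variables, the device comparison is one sentence: performance on the two devices "will be analyzed using pointwise comparisons grouped according to the Garway-Heath structure-function map". It names no test, model, primary point, sector or global index, and no rule for handling several comparisons.
- **XI.2, power.** 80 measurements per device, from 40 clusters of average size 2 for each device, "achieve 87% power to detect a difference between the device means of at least 0". "The standard deviation of subjects is 0.25", with an intracluster correlation of 0.5. "A test based on a mixed-model analysis is anticipated at a significance level of 0.050". The measurement and its unit are not named, and neither section refers to the other's analysis.
- **XI.2, attachment.** "A full version of the power analysis calculation has been attached as an additional document to the IRB", because of formatting difficulty in the transfer. The attachment was not among the documents supplied.
- **VII.E.6, procedures.** Every subject is tested on both devices on the same day, in randomized order.
- **VII.B.11.** The form answers No to a separate written protocol.
- **Enrolment.** I.4 estimates 50 subjects; VI.1 expects 52.

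**The concern.** A claim of being at least as good needs a limit on how much worse the new device may be, and an interval that excludes anything beyond it. The stated plan has neither. It offers comparisons of points grouped by sector and, separately, a test designed to detect a difference. If that test is non-significant, the result fits both true similarity and too little information. If the sectors give mixed results, nothing says which one answers the hypothesis, so the choice could be made after the data are seen.

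The power statement does not settle this. It describes one test on an unnamed variable, and the supplied text does not connect it to anything in XI.1. A reader therefore cannot tell from these documents what the 87% covers, or how well the study could support the claim in I.5.

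**Working it through.** **1. Reproducing the 87%.** Inputs from XI.2: 80 per device, cluster size 2, ICC 0.5, SD 0.25, alpha 0.05 (sidedness not stated).

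- Design effect = 1 + (2 − 1) × 0.5 = 1.5, so effective n = 80/1.5 = 53.33 per device.
- Standard error with separate clusters per device = 0.25 × √(2/53.33) = 0.0484.
- At the printed difference of 0, a two-sided test rejects 5% of the time, so 87% does not reproduce as printed.
- Back-solving: (1.960 + 1.126) × 0.0484 = 0.149. At a difference of 0.15, power = Φ(0.15/0.0484 − 1.96) = 87.25%, or 86.4% to 86.9% with t distributions on 78 or 158 degrees of freedom.
- Other readings need other differences for 87%: 0.134 (one-sided), 0.122 (no design effect), 0.086 (within-cluster variance only).

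The figure thus fits one two-sided test at the full 0.05, with different clusters on each device and a difference near 0.15. It leaves no allowance for several comparisons and makes no use of the pairing. The 0.15 is inferred, not stated.

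**2. The paired contrast.** Assumed, because the supplied text does not say: the clusters are patients with two tested eyes; the correlation r between devices is the same for the same eye and the fellow eye; SD 0.25 and ICC 0.5 apply to the primary variable. Then, for n patients,

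Var(mean device difference) = 0.25² × (1 − r + 0.5 − r)/n.

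- n = 40: SE = 0.0484 at r = 0 and 0.0280 at r = 0.5.
- n = 52: SE = 0.0425 at r = 0 and 0.0245 at r = 0.5.

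At r = 0 and n = 40 the SE equals the one behind the 87%. Any positive correlation makes the paired contrast more precise.

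**3. What non-significance would mean.** With a true difference of 0.10 and 40 patients, the two-sided test is non-significant 46% of the time at r = 0 and 5% at r = 0.5. A non-significant result could therefore be common or rare when a real difference exists, depending on a correlation that the supplied text does not give.

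**4. Non-inferiority power by margin.** True difference 0, one-sided 0.025, power = Φ(margin/SE − 1.96), for r from 0 to 0.5:

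| Margin (assumed) | 40 patients | 52 patients |
|---|---|---|
| 0.05 | 18% to 43% | 22% to 53% |
| 0.10 | 54% to 95% | 65% to 98% |
| 0.15 | 87% to over 99% | 94% to over 99% |

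For example, at 40 patients, margin 0.10 and r = 0: Φ(0.10/0.0484 − 1.96) = Φ(0.106) = 54%. These are normal approximations; a simulation with t intervals at 40 patients and margin 0.10 gave 51.5% and 93.6%, so they run 1 to 3 points high there.

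**The case against.** **The attachment may answer part of this.** It may name the variable and effect, and the printed 0 may be a transfer fault, which XI.2 itself hints at. This stands. A reader might infer that the sample size was computed for a zero difference, or that the 87% is wrong; the documents support neither. But a named variable and effect would still leave XI.1 without a primary contrast, and I.5 without a margin in the form itself.

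**The comparisons may be descriptive.** XI.1 mentions no significance test. A reader might infer severe false-positive inflation: with independent tests at 0.05, 1 − 0.95^6 = 26% for 6 sectors and 1 − 0.95^52 = 93% for 52 points. The documents do not support this as a finding, since they give neither count, do not say that the comparisons will be tested, and field points are correlated (at correlation 0.8 the rates are about 14% and 30%). If the comparisons are descriptive, however, XI.1 does not say which contrast addresses the hypothesis.

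**A margin is not always needed.** Correct: a significant difference in the favourable direction could support better. It cannot rescue the other half of the claim.

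**The study may be adequate.** A reader might infer that it is underpowered. The table does not show that: the answer runs from poor to excellent with the margin, correlation and number of patients. The range of r stops at 0.5, and higher values would improve precision: at r = 0.6, 40 patients and margin 0.10, power is 99.6%. Zero correlation between two same-day tests of one subject is an extreme case. The two-eye structure is also a reading: XI.2 describes its clusters as test orders too, and no supplied passage says that both eyes are tested.

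**The hypothesis concerns detection.** I.5 speaks of identifying field changes. A mean-difference interval does not establish that by itself, which limits what the remedy can claim.

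**Conclusion.** The point holds as a mismatch between hypothesis and analysis. As written, a non-significant result, overall or by sector, cannot support the statement that the headset is as good, and no primary contrast is designated to answer it. This rests on the text of I.5, XI.1 and XI.2 and on none of the assumed figures.

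The supplied text also does not tie the 87% to an analysis in XI.1. The figure fits a single difference test with separate clusters per device and a back-solved difference near 0.15, whereas the design is paired. Whether the attachment supplies the missing variable and effect cannot be judged here.

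The numerical consequence is conditional: under the stated assumptions, non-inferiority power runs from about 18% (margin 0.05, 40 patients, correlation 0) to over 99% (margin 0.15, correlation 0.5). That shows how much turns on an unstated margin, not that the sample is too small. The change should be made; confidence is moderate because the attachment was not available.

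**What to change.** **In XI.1:**
- Name the variable and designate one primary device contrast, a global or sector summary, from the mixed model. Use the within-subject pairing and test order, and eyes within patient if both eyes are tested.
- Report its confidence interval (two-sided 95% for non-inferiority, 90% for equivalence) against a pre-stated, justified margin or agreement criterion, with the favourable direction defined.
- If the primary is a global summary, show sector results beside it, because opposite sector biases can cancel.
- Report other sector results with multiplicity control or label them descriptive. Report points descriptively, with mean differences and limits of agreement.
- State that non-significance will not be read as equivalence. Limit the conclusion to agreement in measured sensitivity unless a detection measure is also analysed.

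**In XI.2:** bring the variable and effect into the form, say what a cluster is, and restate power for the paired contrast over a range of margins, between-device correlations and 40 to 52 patients.

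**Cost:** wording, a justified margin and a short recalculation, with no extra visits or data from each subject. The margin takes clinical argument, sector and point results outside the primary can no longer carry stand-alone claims, and a tight margin may show that the planned number is too small for the claim.

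### Section XI.2 claims 87% power for a device difference of at least 0, where power is only 5%; the printed difference is wrong or cut off

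*Combined protocol and SAP*

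**What the plan says.** Section XI.2 summarises the power calculation. It takes 80 measurements on each device, "which were obtained by sampling 40 clusters for device one and 40 clusters for device two with an average of 2 subjects per cluster", and says that these "achieve 87% power to detect a difference between the device means of at least 0. The standard deviation of subjects is 0.25". The intracluster correlation is given as 0.500. On the test it says: "A test based on a mixed-model analysis is anticipated at a significance level of 0.050". It does not say whether the test is one- or two-sided, and it gives no unit for the difference or the standard deviation.

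The next paragraph of XI.2 says: "A full version of the power analysis calculation has been attached as an additional document to the IRB". It adds that "there was some difficulty with formatting when transferring this calculation from our statistician's text document to the IRB form". The attachment is not among the documents supplied. No other value for the difference, and no non-inferiority or equivalence margin, appears elsewhere in them.

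**The concern.** Power is the probability of rejecting the null hypothesis at a stated true difference. At a difference of 0 the null hypothesis of no difference is true, so that probability is the significance level. Over all differences from 0 upwards, 0 is also where power is lowest, so the words 'at least' do not help: the power guaranteed over that range is 5%, not 87%.

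XI.2 is the only sample-size justification in the supplied text, and the detectable difference is the quantity on which its power figure rests. As printed, a reader cannot see which difference the sample was planned to detect, and so cannot judge whether that difference is small enough to matter. What is at stake is this planning statement. The error does not by itself alter study procedures or the estimate of the device difference.

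**Working it through.** **Inputs, all from XI.2:** n = 80 per device; 40 clusters per device, average size m = 2; SD = 0.25; ICC = 0.500; significance level 0.050; stated power 87%; printed difference 0.

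**Assumptions, not in XI.2:** the design-effect variance formula; one- or two-sided testing (both tried); a normal reference, or a t reference with 158 df (160 measurements minus 2) or 78 df (80 clusters minus 2). Following XI.2, the devices are treated as independent sets of clusters.

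**Step 1: standard error.**

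- Design effect = 1 + (m − 1) × ICC = 1 + 1 × 0.5 = 1.5
- SE = √(2 × 0.25² × 1.5 / 80) = √0.00234375 = 0.0484

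**Step 2: try to reproduce the plan's 87% at the printed difference of 0.**

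- Two-sided: Φ(0/SE − 1.960) + Φ(−0/SE − 1.960) = 0.025 + 0.025 = 0.050
- One-sided: Φ(0/SE − 1.645) = 0.050
- Simulation of cluster data (20,000 runs, t test on cluster means, two-sided): 0.0535

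The figure is not reproduced: power is 5%, against 87% stated. SE drops out when the difference is 0, so no choice of n, SD or ICC changes this.

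**Step 3: find the difference that would give 87%.** With z for 87% power equal to 1.126:

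- Two-sided normal: 0.0484 × (1.960 + 1.126) = 0.149. Any value from 0.148 to 0.151 gives a power that rounds to 87%.
- Two-sided t: 0.150 (158 df) or 0.151 (78 df)
- One-sided normal: 0.0484 × (1.645 + 1.126) = 0.134
- One-sided t: 0.135 (158 or 78 df)

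**Step 4: power at candidate values.**

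| Difference | Two-sided, normal | Two-sided, t 158 df | Two-sided, t 78 df | One-sided, normal |
|---|---|---|---|---|
| 0.13 | – | – | – | 85.1% |
| 0.134 | – | – | – | 86.9% |
| 0.14 | 82.4% | 82.0% | 81.5% | 89.4% |
| 0.15 | 87.3% | 86.9% | 86.4% | 92.7% |
| 0.16 | 91.1% | 90.7% | 90.4% | 95.2% |

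Among two-decimal values, only 0.15 two-sided rounds to 87%, and it does so with the normal or the 158-df reference. With 78 df it rounds to 86%, and simulation at 0.15 gives 86.2%. A three-decimal one-sided value such as 0.134 also fits.

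**Step 5: other variance formulas.** With no design effect, SE = 0.25 × √(2/80) = 0.0395, and 87% two-sided falls at 0.122. If 0.500 were the correlation between devices in 80 pairs, SE = 0.25 × √(2 × 0.5/80) = 0.0280, and 87% falls at 0.086. Neither is the design XI.2 describes, but they show how far the back-calculated value depends on the formula. None brings it to 0.

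**The case against.** **The digits may have been lost when the PDF was read.** If so, the plan contains no error. The supplied text cannot exclude this. Against it, the other decimals in the same paragraph (0.25, 0.500 and 0.050) came through intact, and the form itself reports trouble in the transfer. The form is the more probable source, but the cause remains an inference. Rounding to no decimals is also possible.

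**The form already discloses the trouble and points to a full version.** This is true, and it is a good reason not to question the calculation itself. It does not correct the printed sentence, which is what a reader of the form relies on.

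**A zero difference is ordinary in non-inferiority planning.** The primary hypothesis in section I.5 is that the headset is at least as good as the Humphrey analyzer, and high power at a true difference of 0 is normal for such a test. But XI.2 speaks of power "to detect a difference between the device means of at least 0", and no margin is given. On the stated inputs, that reading would need a margin of 0.149 (one-sided 2.5%) or 0.134 (one-sided 5%); an equivalence test at 5% would need 0.153. The missing number would then be the margin, and the sentence would still be wrong.

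**The back-calculated 0.15 rests on assumptions.** This stands. It depends on the formula, the reference distribution, the sidedness and independent clusters per device, although every subject is tested on both devices (sections VII.E.2 and VII.E.6). The finding does not depend on it: 5% against 87% is enough.

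**Conclusion.** The concern holds. The printed difference of 0 cannot go with 87% power: a difference test at 0.050 has 5% power there, and this needs no assumption beyond the stated level. The remaining inputs agree with each other, since a plausible difference (about 0.15 two-sided or 0.134 one-sided under the design-effect formula) returns the stated power at 80 per device. That makes a lost or rounded number much more likely than a faulty calculation. The fit is best at 0.15 two-sided, but this is a reconstruction and not a documented value.

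Confidence is high that the sentence is wrong as it reads, and lower about how it became so. Severity is minor. Whether the planned difference was a sensible target can be judged only once its value is known.

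**What to change.** In XI.2, replace the printed 0 with the difference used in the full calculation attached to the IRB file, and state its unit and whether the test is one- or two-sided. Take the value from that calculation, not from the back-calculation above. If it does not give 87% on the stated inputs, restate the power. If the attachment turns out to be a non-inferiority or equivalence calculation, say so and print the margin.

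The cost is one sentence and a look at a document already on file. The correction itself requires no change to enrolment or procedures.

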- IX.1 What are the direct benefits to the subject (do not include compensation or hypothesized results)?

 None
- IX.2 What are the potential benefits to society in terms of knowledge to be gained as a result of this project?

 To date, there is no universally accepted head-mounted perimeter for the diagnosis and monitoring of glaucoma. Society may benefit from this study by validation of such a novel head-mounted perimeter. This device may decrease cost and discomfort of visual field testing and increase its accessibility.

X. Privacy & Confidentiality

X.1 What are you doing to protect the privacy interests of the subjects?

All data collected into the research database will only be accessed by the principal investigator (PI) and/or designated key research team members. Patient identifiers and/or data (i.e., name, medical record number) will be collected but will be replaced by study numbers in the analytical file. Subjects' data will be de-identified immediately after completion of the data collection per HIPAA regulations. Subject identifiers will not be viewed by non-study members and will not be published. Subject number identifiers will be used rather than patient names. No other identifiable information will be recorded. All efforts will be made to protect subject's rights to privacy by collecting only the minimum information necessary to meet the aims of this study. Information collected is similar to that which the clinician would encounter for the subject's clinical care.

M&S Technologies receives subject demographic and testing data upon completion of testing using the Smart System VR Headset. This data is stored in a secure, encrypted, HIPAA-compliant database. Subject names are not stored. Instead, Subjects receive encrypted ID codes. Subject data is only shared with M&S-affiliated consultants and service providers, healthcare providers using the Smart System VR Headset, and for law enforcement and judicial proceedings are permitted by law.

- X.2 Are you collecting the Social Security Number of any subjects for any purpose?
- X.4 How will information/data be collected and stored for this study (check all that apply):
 - Paper/hard copy records (hard copy surveys, questionnaires, case report forms, pictures, etc.) Any paper documents
 will be transported directly from the University of Iowa Hospitals and Clinics' Glaucoma clinic to the principal

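### The only test the plan names and powers compares device means, and no measure of paired agreement between the headset and the Humphrey is specified

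*Combined protocol and SAP*

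**What the plan says.** XI.2 is the only place where a test is described. It claims "87% power to detect a difference between the device means" and adds: "A test based on a mixed-model analysis is anticipated at a significance level of 0.050". XI.1 says that Humphrey and headset "performance will be analyzed using pointwise comparisons grouped according to the Garway-Heath structure-function map". It does not say which statistic is used, whether differences are formed within each eye, or what result would count as good enough.

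The stated purpose is broader. The primary hypothesis in I.5 is that the headset is at least as good as the Humphrey at picking up glaucomatous field change. IX.2 refers to a perimeter for diagnosis and monitoring and says: "Society may benefit from this study by validation of such a novel head-mounted perimeter".

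Under VII.E.2 and VII.E.6 each subject is tested on both devices on the same day in randomised order, so paired results will exist. VII.B.11 says there is no separate written protocol, so XI.1 and XI.2 are the analysis plan as far as the documents show it. They nowhere name limits of agreement, a concordance coefficient, classification agreement, sensitivity or specificity.

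**The concern.** Diagnosis and monitoring are decisions about one patient at a time. The difference between device means describes average bias: an eye read too high offsets an eye read too low. Sector grouping does not by itself change this, because signed differences averaged over the eyes within a sector cancel in the same way. Severity subgroups or a margin on the mean would not change it either.

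At stake is the main conclusion. If the average difference is near zero and the test is not significant, the report could present that as the headset performing as well as the Humphrey while the two devices differ substantially in many individual eyes. A larger sample would make the mean more precise but would not reduce that disagreement. VII.B.32 reports no prior studies of this headset, so the documents point to no other agreement evidence.

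**Working it through.** **1. The plan's own figure.** Inputs from XI.2: 80 measurements per device, average cluster size 2, intracluster correlation 0.500, "The standard deviation of subjects is 0.25" (no unit or variable named), and a test "at a significance level of 0.050" (sidedness not stated; two-sided taken here).

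- Design effect = 1 + (2 − 1) × 0.5 = 1.5, so effective n = 80 / 1.5 = 53.3 per device.
- Standard error of the difference = 0.25 × √(2 × 1.5 / 80) = 0.0484.
- XI.2 prints a "difference between the device means of at least 0". At a difference of 0 the power is 5%, the significance level, so 87% is not reproduced.
- At 0.15: 0.15 / 0.0484 = 3.10, and Φ(3.10 − 1.96) = 0.87. With a t distribution on 78 df the power is 86.4%. Solving for 87% gives (1.960 + 1.126) × 0.0484 = 0.149.

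The other inputs therefore fit 87% if the printed 0 is a cut-off 0.15, which is plausible because XI.2 reports formatting trouble in transfer. On either reading, the powered quantity is a difference in means.

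**2. What a test of means can see.** Let d be headset minus Humphrey for one eye. The statistic is the mean of d divided by its standard error. If the true mean of d is 0, a valid test rejects at its significance level whatever the SD of d. This was checked by simulation: 20,000 runs, 40 patients with two eyes, between-eye correlation of d 0.5, and a two-sided t test on patient mean differences. The SDs are assumptions.

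| Per-eye SD of d | Runs rejecting | 95% limits of agreement (±1.96 × SD) |
|---|---|---|
| 1 dB | 5.1% | ±2.0 dB |
| 3 dB | 5.3% | ±5.9 dB |
| 5 dB | 5.0% | ±9.8 dB |
| 8 dB | 4.9% | ±15.7 dB |

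With every eye wrong by exactly +6 or −6 dB at random, independently between eyes, the test rejected in about 5.5% of runs.

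**3. Illustration of the gap.** Assumptions, none given in the documents: true mean difference 0, normal differences, 40 patients with two eyes correlated 0.5 (design effect 1.5), and a per-eye SD of 4 dB with a range of 2 to 6. The 3 dB cut-off is also only illustrative.

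- CI half-width for the mean = 1.96 × SD × √(1.5 / 80)
- Limits half-width = 1.96 × SD
- Share of eyes beyond 3 dB = 2 × (1 − Φ(3 / SD))

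| SD | CI for the mean | Limits of agreement | Eyes beyond 3 dB |
|---|---|---|---|
| 2 dB | ±0.54 dB | ±3.92 dB | 13% |
| 4 dB | ±1.07 dB | ±7.84 dB | 45% |
| 6 dB | ±1.61 dB | ±11.76 dB | 62% |

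**4. Can the planned data support limits of agreement?** The 95% CI half-width for each limit is about 1.96 × SD × √(1/n + 1.96² / (2(n − 1))). That is 0.38 SD for 80 independent eyes, 0.46 SD at effective n 53.3, and 0.53 SD if only 40 patients count. At SD 4 dB these are about 1.5, 1.8 and 2.1 dB.

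**The case against.** The strongest reply is that XI.2 is a sample-size rationale, while the analysis is described in XI.1, whose pointwise comparisons could be made within each eye and could include an agreement measure. A reader might infer that the plan will not estimate agreement. The documents do not support that: XI.1 is silent on the statistic, and silence is not exclusion. Sector grouping could also reveal bias confined to one location. What stands is that no agreement measure is specified and the only test named is on means.

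Three other inferences also go too far.

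- *That a null result would establish equality.* Non-rejection is not equality, and the plan has no margin or rule for declaring it. The risk is that a null result is read that way.
- *That the devices would disagree in most eyes.* At the central assumption 45% of eyes differ by more than 3 dB. More than half requires an SD above 3 / 0.6745 = 4.45 dB, and the documents give neither a variability in dB nor a clinical cut-off.
- *That two eyes per patient are planned.* XI.2 speaks of two subjects per cluster and then describes clusters as test order. Enrolment is given as 50 in I.4 and 52 in VI.1, not 40.

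It is also fair to say that limits of agreement do not answer the hypothesis in I.5, which concerns detection. A headset that outperformed the Humphrey would also disagree with it. VII.E.6 describes a single test per device, so wide limits would include both devices' test-retest variability and could not be attributed to the headset alone. These points restrict what the limits can show, but they do not make the mean difference sufficient.

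**Conclusion.** The point holds as a gap in the specified analysis and should be corrected. Following XI.2 as written yields an estimate of average bias and a test that is blind to paired errors that cancel; XI.1 does not commit to anything that would reveal them. That blindness follows from the form of the test and does not depend on the assumed SD, the unit, the number of eyes, or whether the printed difference of 0 is a transfer fault.

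The size of the gap does depend on assumptions. Under those in the illustration, an interval of about ±1 dB for the mean would coexist with limits of nearly ±8 dB, and the ranges shown are as much as can be said without a documented SD of paired differences. The full power calculation, which XI.2 says is attached separately, was not available; it is described as a power calculation, not as an analysis plan.

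**What to change.** Amend XI.1 as follows.

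- Keep the mean-difference model as the bias component.
- Alongside it, for the whole field and for each Garway-Heath sector, specify the mean paired headset-minus-Humphrey difference and its 95% limits of agreement, with confidence intervals that allow for clustering if both eyes of a patient are used.
- Add a plot of difference against average, to show whether bias or spread changes with sensitivity.
- State that any claim of validation, or of performing as well as the Humphrey, will rest on the limits as well as the mean.
- State that limits from single tests include the test-retest variability of both devices and do not by themselves test detection of glaucomatous change.

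The documents give no acceptable width for the limits. If the investigators want to judge the limits against one, they would have to justify and fix it before seeing the data.

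The cost is analysis wording: the same paired tests are used, with no added visits or procedures. The downside is that the conclusion may be less favourable to the headset.
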